A participant's study information will not be released without the written permission of the participant. All study-related information will be stored securely at the study site. All participant information will be stored in locked file cabinets in locked rooms, i.e., access is limited to study staff. All study data collection, process, and administrative forms and other reports will be identified by a coded number to maintain participant confidentiality. All records that contain names or other personal identifiers, such as locator or informed consent forms, will be stored separately from study records identified by a code number. All databases will be secured with password-protected access systems. Forms, lists, logbooks, appointment books, and any other listings that

link participant ID numbers to other identifying information will be stored in a separate, locked file in an area with limited access.

Consent Procedures

The consent procedures are detailed above and the consent forms can be found in the Appendix (Appendices 5, 6, and 7). The signed consent forms will be kept in a lock box at the FGH office in Quelimane, separate from the transcripts of the interviews. The consent forms will be kept for seven years, at which point they will be burned to ensure that no one will be able to link any consents to participants.

Evaluation of benefits and risks

Adverse events

Risks to the subjects (both intervention and control group and family members): The level of risk associated with this research is expected to be minimal for all participants. Potential psychological discomfort may occur when administering the survey for participating couples, as many of the questions are personal and have to do with a stigmatized infectious disease. All participants are able to decline to answer any question that they deem uncomfortable.

Adverse Experience: We do not anticipate any adverse events as a result of this study, however study participants will be provided with a telephone number and instructed to contact study clinicians to report any serious AEs they experience.

Protection against risks: The study protocol and training manuals will include strict guidelines for conducting the survey and recording the data in a confidential manner. All study staff will receive formal responsible conduct of research training per NIH, VUMC, and Mozambican Ministry of Health guidelines. Participants may withdraw from the study for any reason at any time.

Benefits

For serodiscordant infected couples there is a possibility that storytelling engagement with family members will result in them gaining additional psychosocial support and education for their treatment. For these patients, they could experience improved health outcomes. The results of this evaluation may help us to offer better services for discordant couples who access services at the study clinics and throughout Mozambique. There could be a benefit to Mozambican society through improved health programs for people living with HIV.

12. Limitations

Our sample size of 35 couples in each arm is small, which limits our ability to detect a small change in behavior among couples. However, we believe this pilot will allow us to detect signals of an interventions success, which we can subsequently use to fund a larger trial.

13. Dissemination Plan

Results from this study will be collected into a report and will be shared with MISAU and the DPS. The results will also be disseminated to government officials and physicians working in these communities. If results are deemed by the authors to be potentially of interest to a wider scientific audience, we would plan on sharing these data in manuscript form, after obtaining appropriate clearances.

14. Budget

Description	TOTAL		Study Details	
	USD	MZM	Price per unit/ person (USD)	Number of people/ units
Human Resources	11,150	669,000		
Project Officer	3,000	180,000	3,000	1 (20% effort)
Study Counselor	3,000	180,000	3,000	1
Interviewers for in-depth qualitative interviews	3,150	189,000	35	2(p)*45(d)
Storytelling implementer	2,000	120,000	2,000	1
TRAVEL & TRANSPORT	1,130	67,800		
maintenance for car/gas	900	54,000	45	20
bicycle repair kit	90	5,400	45	2
bicycle for storyteller	140	8,400	140	2
TRAINING/PROJECT ACTIVITIES	9,045	542,700		
Training for protocol implementation				
Per diem (food)	1,625	97,500	65	5(p)*5(d)
Venue hire (day)	500	30,000	100	5(d)
Training materials	1,000	60,000	1,000	1
Training for Storytellers supporters				
per diem (food)	1,300	78,000	65	10
Venue hire (day)	400	24,000	100	4
Training Materials	1,000	60,000	1,000	1
Supervision Activities				
Per diem (food)	1,820	109,200	65	4(d)*7(m)
Hiring of transport to/from site	1,400	84,000	100	14(d)
OTHER	1,745	104,700		

Photocopies of consent forms and questionnaire	500	30,000	0.25	2,000
basic nokia phone & credit for study counselor	195	11,700	15	13
Urine assay tests	1,050	63,000	5	210
Total of all costs	23,070	1,384,200		
Contingency 10%	2,307	138,420		
TOTAL	25,377	1,522,620		

15. Timeline

Month	Activities/Description
Month 1	Hire personnel & train them in PrEP specific protocols and delivery of Storytelling intervention
Month 2-7	Recruit of discordant couples in ANC
Months 2-9	Delivery of storytelling intervention to couples
Months 2-9	Collect quantitative survey data at baseline and 3 months
Months 5-9	Collect qualitative data from intervention couples
Month 7	Coding and data analysis of qualitative data
Month 9-10	Conduct quantitative data analysis of survey data and adherence measures
Month 11-12	Write up R01 grant to conduct a larger healer-initiated counseling and testing project.
Months 11-12	Disseminate findings via community meetings in Zambézia, to the Ministry of Health in Maputo, and PEPFAR partners.

16. Statement of Conflict of Interest

As the Principal Investigator, I will be responsible for the relevance and quality of the project research, and for the confidentiality and anonymity of the participants.

Statement of conflict of interests

[figure not shown]
I, [name], as Principal Investigator of the Project entitled "*Partners-based HIV Treatment for Sero-concordant Couples attending Antenatal Care: Increasing family-based support for PrEP adherence among discordant couples through storytelling*", declare that I am an employee of the Vanderbilt University Medical Center in Nashville, Tennessee, USA, working closely with Friends in Global Health (FGH) in Mozambique.

I am engaged in the interview and survey design process, the evaluation design approach, as well as in the production of the pilot intervention and evaluation protocol. I will also contribute in the analysis and presentation of the results of the above-mentioned evaluation, in collaboration with:

- VUMC's Institute of Global Health: non-profit entity committed to building capacity in low-resource settings through interdisciplinary global health educational and training programs, technical assistance to government and civil sector organizations, and implementation science and research in order to improve health and equity.

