2. Family members (as defined by relatives living in the participants’ household or relatives the participants identify as living in the study community) will be eligible to participate if: i) they participated in at least one of the storytelling sessions; ii) are 18 years of age or older; iii) are able to give informed consent; and iv) are willing to participate in the interview.

c. Exclusion Criteria:

1. Couples will not be eligible to participate in the study if the woman is not pregnant, if she is HIV-positive or if her partner is not HIV-positive, if either person is younger than 18 years, if one member of the couple is unwilling to enroll in PrEP/ART or consent to the infant record search, or if one member of the couple is unable or unwilling to give informed consent for any reason.
2. Family members will not be eligible to participate in the study if they do not participate in at least one storytelling session, if they are younger than 18 years old, if they are unable or unwilling to give informed consent for any reason (e.g. have been drinking or show other signs of mental limitations), or if they are not willing to participate in the interview.

d. Calculations of Sample Size:

Objectives 1 & 2: Our pilot will involve 70 couples (70 HIV-negative pregnant women and their HIV-positive male partners; 35 couples in each arm) from a single clinic. Limited data on PrEP in Mozambique suggest 55% of pregnant women were not retained at 3 months after PrEP initiation. Given our sample size of 70 women and a 5% type I error, we will have 82% power to detect a RR of 0.40 for not being retained. Should there be evidence the intervention effect is similar for men and women with regards to retention, the two groups can be analyzed together to further improve power to detect RRs closer to 0.50. We do not have estimates of Tenofovir levels among PrEP users, but other studies indicate as many as 70% may have no active drug detected.[76]

Given our sample of 70 women and a 5% type I error, we will have 85% power to detect a RR of 0.50 for no detectable drug level.

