Family members of intervention participants who are nominated for participation by the discordant couple will be recruited by the study assistant at the home of the discordant couple (already consented and enrolled in the study). The discordant couple will ask their family member(s) to stay home or invite their family member(s) over during a pre-arranged time slot, and the study assistant will meet them there to explain their potential participation in the trial and to obtain the family members' consent (if applicable).

g. Patient participant retention and withdrawal:

Participant retention and withdrawal from clinical care: As per standard clinic procedure, peer educators will track all patients who miss appointments at the health facility selected as study site. The peers will document patients as terminating clinical care services if they: (1) discontinued

services due to death; (2) transferred their care to another clinic; (3) are lost to follow-up (defined as being >60 days late for a clinic appointment); or (4) discontinue for any other reason, including patient choice.

[figure not shown]
Participant retention and withdrawal from pilot: Study participants can choose to discontinue participation in the study and decide that their medical data and/or study data cannot be used in the analysis at any time by formally communicating their decision to the study manager.

8. Methods

a. Study Procedures for patients

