as six weeks after birth. If the infant seroconverts, s/he is provided ART for life. Follow-up at respective clinic points for mother and infant continues for 18 months or until the mother ceases breastfeeding. Relevant medications are also offered free of charge in the adult HIV clinic to male partners (Figure 2). If the woman seroconverts at any point during the study, HIV-specific counseling and support, provision of cotrimoxazole prophylaxis, Isoniazid Preventive Therapy, and universal ART are provided free of charge (currently all adults are offered ART, regardless of CD4 cell count).[78] Viral load testing is routinely available for all ART-treated children and adults. The only other procedure that is not considered SOC, but will be conducted with all consenting study participants, including in the control arm, is the monthly measuring of PrEP (tenofovir) drug level via urine assay testing, which will be explained to all participants prior to consenting to study enrollment. **Storytelling Intervention:** The participants randomized to the intervention arm will receive all of the SOC services and PrEP drug level testing (for female) as described above (i.e., will receive the same SOC clinical services as those couples randomized to the control arm). In addition, the individuals randomized to intervention arm will be invited to participate in three storytelling sessions with their partner and family members (of their choosing). The stories will be told by theater-trained community members who will deliver the narratives in the first person, each person playing/voicing an assigned character at the couple's home (or in a preferred location chosen by the participants). Each narrative will last 12-15 minutes. At the conclusion of the narrative, the facilitators will open up a discussion with those listening to the story. They will engage the family in a discussion, asking them about the storyline they just heard. They will ask questions to specifically probe for reactions to events and difficult characters/interactions. They will lead the discussion about ways the main characteristic (discordant couple) overcome challenges in adherence to medication; seeking to see if there are ways the messages can be related to their own lives (Appendix 2). We will conduct the first two stories in the first month of enrollment to try and influence participants' behavior/thinking prior to their first follow-up visit for medication pickup (in an effort to assess storytelling's impact on attendance at visit).

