
Procedures for drug level measurement.

Every time the couple returns for a medication pick up the woman on PrEP will be asked to provide a small sample (1ml is sufficient) of urine for the tenofovir assay. If a participant misses a medication pick-up, or if their male partner picks up their medication, the study assistant will bring the urine assay to the participant's home to complete the test. The test is simple to use: like a pregnancy test, the patient only has to urinate on a testing stick to identify the presence of the medication.

Study procedures for the qualitative interviews

Qualitative interviews will be conducted at least 4 months after the couple and their indicated family members have been enrolled in the study. We will purposely select roughly equal numbers of participants (including couples and their family members) who were adherent to PrEP/ART and those who have not been adherent to medication (measured via ART pick-ups and PrEP drug level assays). Interviews will be arranged by the study assistant and can be completed either at the health facility or at the home of the participant (depending on the preference of the participant). The qualitative interviews will only be completed one time, with no additional follow-up for the

participant.

Measurement of Results

Objective 1: Using interviewer assisted surveys, we will collect male and female partner (1) depression;[79] (2) partner and family support;[60, 80] (3) empathy;[81] (4) relationship satisfaction;[82] (5) PrEP adherence knowledge; and (6) motivation/perceived ability to adhere to medication[83] at baseline and three months.

Objective 2: Routinely collected demographic, community-based social support, and PrEP/HIV care and treatment data will be used in the analysis. Select demographic, clinic, and laboratory data (see Appendix 1) from these forms are entered routinely into OpenMRS (an electronic medical record “EMR” system) at FGH-supported sites. We will collect data about participant eligibility among those who attend ANC services including reasons for refusal among eligible participants. Lastly, we will assess PrEP drug levels using urine analysis (not considered standard of care) among participants in both groups (control and intervention).

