Objective 2: Primary analyses will follow an intent-to-treat protocol. We operationalize the outcomes in the negative (e.g., not retained, no active drug levels, no virologic suppression) such that the risk ratios (RR) for the intervention effect will be <1.0 if effective. We will estimate the intervention effect on dichotomous endpoints using separate *modified Poisson regression* models for each outcome to estimate risk ratios and 95% confidence intervals. Modified Poisson models use a robust standard error to estimate the RR with unbiased confidence intervals to avoid convergence problems with log linear models and to improve interpretation over logistic regression since the outcome is relatively common ($>30\%$). If we still encounter problems with model convergence due to the small sample size, we will utilize logistic regression models instead. We will use GEE models with an interaction term between intervention arm and gender as described in Aim 1. We will also explore intervention effect modification and adjustment for other covariates as described in Aim 1.

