37. Patient status (active, default, LTFU, transfer, or death) every month after enrollment;
38. Dates of all PrEP/ART pick-ups
39. Dates of all next scheduled PrEP/ART pick-ups;
40. Dates of all clinic visits
41. Dates of all next scheduled clinic visits;
42. Date cotrimoxazole (CTX) prescribed;
43. Patient reported use of intravenous (IV) drugs;
44. Patient reported use of tobacco;
45. Patient reported use of alcohol;
46. Estimated due date of pregnant female patient;
47. Initiation of any family planning method (Depo, pill, intrauterine device (IUD), implant, condoms, lactational amenorrhea [LAM], tubal ligation, vasectomy [male partner]), and date of initiation;
48. Continuation of any family planning method (Depo, pill, IUD, implant, condoms, LAM, tubal ligation), and date of continuation;
49. Final patient outcome status and date of final status:
 - a. Transfer out of care at that facility, and date of transfer out;
 - b. Death, date of death recorded, cause of death where available;
 - c. LTFU, date of most recent visit (LTFU defined as not returning for >60 days past last scheduled appointment / pick-up date);

- 50. Number of babies with this pregnancy;
- 51. Concentration of PrEP in patient urine;
- 52. Monthly patient self-report of adherence using this scale:

(for each baby, if multiple live births this pregnancy)

- 53. Date of birth of infant(s);
- 54. Infant status at birth (alive, dead);
- 55. Sex of infant(s);
- 56. Weight of infant(s) at birth, and at all other clinic visits, and date of documentation;
- 57. Whether infant(s) received ART prophylaxis after birth, date of start, and type of ARV;
- 58. Data on infant feeding practices where available;
- 59. Date of any PCR testing for infant(s), and test results;
- 60. Date of any HIV rapid testing for infant(s), and test results;
- 61. Data on discharge from CCR services (transfers, referrals, abandoned, died), and date;
- 62. Health status of child(ren) at 18 months (alive, dead);
- 63. HIV health status of child(ren) at 18 months (HIV-positive, HIV-negative)

ANC-specific indicators (aggregated data, from OpenMRS and DHIS databases)

- 64. Number of pregnant women who arrived for first ANC appointment;
- 65. Number of pregnant women who know their serostatus, known positive;
- 66. Number of pregnant women who know their serostatus, recently tested;
- 67. Number of pregnant women who received HIV test results in ANC, first test (positive, negative, and indeterminate results);

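### Does the plan need to say whether a partner's collection of the woman's PrEP counts as her own retention?

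*Combined protocol and SAP*

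**What the plan says.** Section 7.d takes its control risk from limited local data, which "suggest 55% of pregnant women were not retained at 3 months after PrEP initiation", and concludes "we will have 82% power to detect a RR of 0.40 for not being retained". Section 10, Objective 2, lists the dichotomous endpoints in negative form ("e.g., not retained, no active drug levels, no virologic suppression") without deriving any of them.

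Other passages bear on what retention means:

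- Section 7.g, on retention and withdrawal, lists when peers record that a patient has left care: death, transfer, patients who "are lost to follow-up (defined as being >60 days late for a clinic appointment", or discontinuation for another reason.
- Appendix 1, item 37, records each patient's status monthly (active, default, lost, transferred or dead). Item 49c words loss a little differently: "LTFU defined as not returning for >60 days past last scheduled appointment / pick-up date".
- Appendix 1, item 38, is "Dates of all PrEP/ART pick-ups". Items 40 and 41 hold clinic visit dates and the next scheduled visits. No item records who collected.
- Section 8.a times the first two stories before the first follow-up visit, to look at their "impact on attendance at visit".
- Section 8.a also provides for home urine testing: "If a participant misses a medication pick-up, or if their male partner picks up their medication, the study assistant will bring the urine assay".

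**The concern.** The protocol names a situation in which two reasonable readings of retention can disagree. If a woman attends at month 1 and her partner collects at months 2 and 3, pick-up dates show her as retained, while her own attendance may not. The study assistant learns of each such collection, because it triggers the home test, yet no listed field stores it.

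The disagreement need not be equal between arms. Study Question 2 asks whether the intervention raises partner support, and the background names travel to the facility as a barrier that families can ease. If storytelling led partners to collect more often, a pick-up definition could show a benefit with women's attendance unchanged. An attendance definition could hide a real gain in supply. With 35 women per arm, a few women could decide which side of 0.05 the result falls, and the choice could be made after the data are seen.

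**Working it through.** **Inputs.** From section 7.d: 35 women per arm, control risk 0.55, RR 0.40 (so intervention risk 0.22) and 5% type I error, taken as two-sided. The documents give no rate of partner collection; every share below is an assumption.

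**Stated power.** With pooled variance under the null:

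- mean risk = (0.55 + 0.22)/2 = 0.385
- SE0 = √(2 × 0.385 × 0.615 / 35) = 0.1163
- SE1 = √((0.55 × 0.45 + 0.22 × 0.78)/35) = 0.1094
- power = Φ((0.33 − 1.96 × 0.1163)/0.1094) = Φ(0.93) = 82.4%

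The stated 82% reproduces.

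**How few women matter.** 0.55 × 35 = 19.25 and 0.22 × 35 = 7.7, rounded to 19 and 8. Women retained only through partner collection are moved to not retained in the intervention arm:

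| Not retained, control vs intervention | RR | p, pooled z | p, log-RR Wald |
|---|---|---|---|
| 19 vs 8 | 0.42 | 0.007 | 0.013 |
| 19 vs 9 | 0.47 | 0.015 | 0.022 |
| 19 vs 10 | 0.53 | 0.029 | 0.038 |
| 19 vs 11 | 0.58 (95% CI 0.33 to 1.03) | 0.053 | 0.063 |

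Three women cross the threshold from this starting point. The estimate stays on the same side of 1.

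**Equal attendance, unequal collection.** Let 55% not attend in both arms, and let partners collect for a share q of non-attenders. The pick-up risk is 0.55 × (1 − q). The chance of a significant result favouring the intervention comes from exact enumeration of two Binomial(35) counts with the pooled z test:

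| q control | q intervention | Pick-up RR | Chance |
|---|---|---|---|
| 0 | 0 | 1.00 | 2% |
| 0 | 10% | 0.90 | 6% |
| 0 | 20% | 0.80 | 13% |
| 0 | 30% | 0.70 | 26% |
| 0 | 40% | 0.60 | 44% |
| 10% | 20% | 0.89 | 6% |
| 10% | 30% | 0.78 | 14% |
| 10% | 40% | 0.67 | 28% |

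With equal shares the factor (1 − q) cancels and the RR stays 1.00. The size therefore depends on the assumed gap between arms.

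**Planned collection effect, attendance reading.** If collection follows 0.55 vs 0.22 and partners make shares rC and rI of the collections, the attendance risks are 1 − 0.45(1 − rC) and 1 − 0.78(1 − rI). Shares of 10%/10% give 0.595 vs 0.298, RR 0.50, power 71%. Shares of 10%/20% give RR 0.63, power 45%. Shares of 10%/30% give RR 0.76, power 22%.

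**The example against the written threshold.** Take 30-day months and monthly pick-ups. A woman last seen on day 30 and next due on day 60 is 90 − 60 = 30 days late at month 3. That is not more than 60, so she is not lost by either reading. To be lost by attendance she must stay away beyond day 60 + 60 = 120, and the loss must then be dated back to her last visit.

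**What the listed data allow.** Pick-up dates (items 38–39) and clinic visit dates (items 40–41) are separate, so both readings can be attempted. Enrolment and PrEP start dates (items 19 and 20) are both held, so either clock can be used.

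**The case for a change.** The strongest reply is that the written threshold cannot be the whole definition. A woman who never returns after starting PrEP is due on day 30 and is exactly 60 days late on day 90, so she too is not yet lost. A 55% failure rate at 3 months therefore implies a stricter rule, back-dating, or use of the default status, which is undefined. Under any of these the two readings can part. Moreover, comparing visit dates with pick-up dates reveals partner collection only if such a collection is not also logged as the woman's visit, and the documents do not say. Because this pilot is meant to support a larger trial, the meaning of its signal matters.

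The missing derivation therefore stands as a fact, and writing it down before analysis would be tidier. The step from there to a faulty result does not stand:

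- The background passage on transport is at least as compatible with the woman travelling more safely and attending more. Section 8.a ties HIV testing to medication pick-up, which implies her presence at some of them. The story themes in Appendix 2 describe emotional and household support, not collection by the partner.
- If retention means still being supplied with drug, extra collection by partners is an effect of the intervention. The percentages above are then not false positives; the issue is interpretation.
- The other powered outcome, urine tenofovir, is tested at home when the partner collects, so drug exposure is still measured.
- A shift of three women can cross 0.05 for many binary outcomes with 35 per arm. Section 12 already acknowledges the small sample.

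**Conclusion.** No change is called for. The plan leaves out a derivation, but an analyst has a natural one to hand: active in care at 3 months, using the section 7.g categories and the monthly status, with the reading adopted named in the report. Where visit and pick-up dates differ, the alternative reading can be shown beside it.

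The possible size runs from nothing, if partner collection is absent or (with equal attendance) equally common in the two arms, to a pick-up RR of 0.60 with no change in attendance, if partners collect for 40% of intervention non-attenders (0.40 × 19.25, about 8 women) and none in control. The documents support no particular point in that range. The conclusion assumes that partner collection is uncommon or not strongly tied to arm, and that visit dates are not simply copied from pick-up dates. The 82% power figure is correct for the risks it states under either reading.

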Analyses will follow an intent-to-treat protocol. We will estimate the intervention effect on mean outcome scores using separate *linear regression* models for each outcome. If any outcome demonstrates a skewed distribution, we will consider score transformation. Generalized estimating equations (GEE) with an exchangeable working correlation structure will be used to account for clustering within couples. Each model will also include an interaction term between treatment arm and gender to identify gender-specific effects. Given the small sample size and low power of homogeneity tests, if the p-value for the interaction term is ≥ 0.20 , we will also report the

intervention effect for men and women combined (no interaction term). We will not be powered to detect other intervention effect modifiers unless gender is not a modifier, in which case we will explore modification by baseline values of the outcome being analyzed (e.g., is the intervention more effective at improving partner/family support among participants with low partner/family support at baseline), again using an interaction p-value <0.20 as our criteria for evidence of modification of the intervention effect. Finally, given the small sample size of this RCT, it is possible potential confounders remain imbalanced between treatment arms. We will repeat the above analyses (which already include gender), further including age and the baseline value of the outcome being analyzed, to adjust for residual confounding. The small sample, however, precludes from including additional covariates beyond these.

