Secondary analyses will also follow intent-to-treat protocol, again operationalizing the outcomes in the negative (monthly count of missed doses; monthly nonadherence) such that the rate or risk ratios will be <1.0 if the intervention is effective. We will estimate the intervention effect on the count of monthly missed doses using a negative binomial regression model to account for overdispersion due to an excessive amount of zero missed doses (perfect adherence). In addition to clustering of couples, each participant will have up to three observations (one for each month of follow-up). Participants LTFU will only contribute an observation for each completed month of follow-up for which there is a pill count, otherwise they are censored. Similarly, self-reported monthly nonadherence is likely to be heavily skewed with a large proportion of 0% nonadherence. As this is inherently a continuous measure (rather than a count), we will dichotomize as 0% nonadherence vs. $>0\%$ nonadherence and each participant will contribute an observation for each completed month of follow-up. A sensitivity analysis will be performed with dichotomization at $\leq 10\%$ nonadherence vs. $>10\%$ nonadherence. As for the prior analyses, we will utilize GEE models (accounting for clustering of couples and repeated measures on individuals) with an interaction term between intervention arm and gender and will explore modification and adjustment for other covariates as described in Aim 1.

Objective 3: Following completed interviews, audio files will be transcribed by the interviewer, and the PI will code and analyze the interviews using MAXQDA 12® software. Framework Analysis will be used to identify responses to questions about the drivers, core facilitators, and barriers to intervention acceptability and success using grounded theory.[86] Two code maps will be developed to categorize data: (1) to understand the social, structural, and informational drivers, facilitators, barriers to recruiting, providing services for, and supporting discordant couples in

couple-based ANC and post-natal care; and (2) to understand concepts of “best-practice” for scaling up and implementing these services, particularly in regards to family engagement and using stories for educational purposes.

11. Ethical Considerations

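### Aim 1 leads with a model that omits the baseline score and names no primary analysis; the baseline-adjusted GEE model already planned should be named primary

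*Combined protocol and SAP*

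**What the plan says.** Section 10 (Quantitative Analyses, Aim 1) lists six scale outcomes. Each gets its own linear model of mean score, fitted by GEE with an exchangeable correlation within couples and an arm-by-gender interaction. That first model has no baseline score.

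The same account closes with a second round of models that differ from the first in two covariates, described as "further including age and the baseline value of the outcome being analyzed, to adjust for residual confounding". The reason given is chance imbalance in a small trial.

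Neither Aim 1 model is called primary. Section 10 uses the labels primary and secondary for analyses only under Objective 2. The two Objective 2 paragraphs refer back to Aim 1: "We will also explore intervention effect modification and adjustment for other covariates as described in Aim 1" and, for the secondary outcomes, "will explore modification and adjustment for other covariates as described in Aim 1".

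Section 8 (Measurement of Results, Objective 1) has both partners surveyed on all the scales twice; the list ends "motivation/perceived ability to adhere to medication[83] at baseline and three months". The baseline score is therefore in hand. Section 10 does not say whether the outcome score is the 3-month value or the change from baseline.

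**The concern.** Randomization already protects the comparison from systematic confounding. What the baseline score mainly adds is the removal of outcome variation that was present before treatment, and that benefit does not wait for a visible imbalance. Treating it as a late check for residual confounding puts the estimate that is likely to be less precise first. Section 12 describes a small pilot meant to detect signals that can support a larger trial, so precision on these scales matters.

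The missing label is a second, smaller problem. The order of the text suggests that the unadjusted model leads, but nothing says so. Each scale will have two estimates, and a reader cannot be sure which is the main result.

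**Working it through.** **The plan's own figures.** Section 7d gives power for Objective 2 only. With 35 women per arm, two-sided 5% and pooled variance, power = Φ{[(p1 − p2)√n − 1.96√(2p̄(1 − p̄))] / √[p1(1 − p1) + p2(1 − p2)]}.
- Retention, 55% vs 22%: (1.952 − 1.349)/0.647 = 0.932, power 82.4% (stated 82%).
- No detectable drug, 70% vs 35%: (2.071 − 1.384)/0.661 = 1.038, power 85.0% (stated 85%).

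Both reproduce and neither is disputed. No SD, target difference or power is given for any Aim 1 scale, so what follows is in relative terms.

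**Inputs.** 70 couples, 35 per arm (Section 7d). Two added covariates, baseline score and age (Section 10). The correlation r between baseline and 3-month scores is not in the documents; 0.3, 0.5 and 0.7 are assumed. Equal variances at the two times are assumed.

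**Cost of two covariates.** Expected inflation of the variance is 1 + 2/(70 − 2 − 2 − 1) = 1 + 2/65 = 1.031. With 50 couples completing the 3-month survey it is 1 + 2/45 = 1.044.

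**If the outcome is the 3-month score.** Variance ratio, adjusted to unadjusted = (1 − r²) × 1.031.

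| r | Variance ratio | Reduction | SE ratio |
|---|---|---|---|
| 0.3 | 0.91 × 1.031 = 0.938 | 6% | 0.969 |
| 0.5 | 0.75 × 1.031 = 0.773 | 23% | 0.879 |
| 0.7 | 0.51 × 1.031 = 0.526 | 47% | 0.725 |

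For scale: the difference detectable with 80% power in one gender is (1.96 + 0.84) × √(2/35) = 0.67 SD unadjusted. Multiplied by the SE ratios it becomes 0.65 / 0.59 / 0.49 SD.

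**If the outcome is the change score.** The unadjusted variance is proportional to 2(1 − r) and the adjusted to 1 − r², so the ratio is (1 + r)/2 × 1.031.

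| r | Variance ratio | Reduction |
|---|---|---|
| 0.3 | 0.65 × 1.031 = 0.670 | 33% |
| 0.5 | 0.75 × 1.031 = 0.773 | 23% |
| 0.7 | 0.85 × 1.031 = 0.876 | 12% |

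On untransformed scores, a linear model that contains the baseline score gives the same arm effect for the 3-month score as for the change score. The ambiguity therefore affects only the unadjusted model.

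**Downside, against the 3-month score.** At r = 0 the SE ratio is √1.031 = 1.015. Break-even is r = √(1 − 1/1.031) = 0.17, or √(1 − 1/1.044) = 0.21 with 50 completing couples.

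**Simulation check.** The exchangeable GEE model was simulated with 35 couples per arm, within-couple correlation 0, 0.3 or 0.6, no gender difference and age unrelated to outcome (4,000 runs per setting). The ratio of standard deviations of the estimated effect was 1.008 to 1.013 at r = 0, 0.993 to 0.995 at 0.17, 0.964 to 0.971 at 0.3, 0.862 to 0.889 at 0.5 and 0.719 to 0.736 at 0.7. This agrees with the formulas and puts the cost at r = 0 at about 1 to 1.5%.

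**Two unlabelled estimates.** Under no effect, the two test statistics for a 3-month score have correlation about √(1 − r²) = 0.954 / 0.866 / 0.714. The chance that at least one exceeds 1.96 in absolute value is then 6.4 / 7.3 / 8.3% per scale. For change scores the correlation is √((1 + r)/2) = 0.806 / 0.866 / 0.922, inside the same range, so about 6 to 8% covers both readings.

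**The case against.** The strongest reply is that nothing here is invalid. Both models are written down in advance, the unadjusted comparison is unbiased under randomization, and the order of the text suggests which model leads. All of that stands and limits the harm. The 6 to 8% figure is also a ceiling: it applies only if someone takes whichever estimate is favourable, and the plan does not say that anyone will.

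A second reply is that the gain is assumed. That also stands: r is not in the documents and the outcome is not defined as a 3-month or a change score. A reader might infer that adjustment makes 70 couples worth about 133 (70/0.526). That is one end of the range. It needs r = 0.7, a 3-month score and complete surveys; at r = 0.7 under change scores the reduction is about 12%, not 47%.

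A reader might also infer that the combined effect should be shown whatever the interaction p-value, since the plan reports the "intervention effect for men and women combined (no interaction term") only when that p-value is at least 0.20. The documents do not support calling this a defect. The rule is prespecified with a reason ("Given the small sample size and low power of homogeneity tests"), and gender-specific effects are always reported. Always pooling would show an average more often when the sexes truly differ, and would make no estimate more precise. Nor can it be confirmed that the support scale is put to both partners on the same footing: one of its two cited instruments is not printed in Appendix 3. The remark in Section 7d, "Should there be evidence the intervention effect is similar for men and women with regards to retention", concerns retention only and does not settle the matter for the scales. Showing the combined effect in every case is a reporting preference.

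**Conclusion.** The point holds as one of precision and labelling for Aim 1. The plan leads with the model that is likely to be less precise, adds the baseline score last for a secondary reason, and names no primary analysis. Under either reading of the outcome, the adjusted model is more precise across the assumed range r = 0.3 to 0.7. Against a 3-month score it loses only when r is below about 0.17 (0.21 with 50 completing couples), and then by at most about 1.5% in standard error with all 70 couples observed.

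The percentages rest on assumed r, equal variances at the two times, a linear relation and complete 3-month surveys. The harm is modest. The documents do not support a stronger claim that the unadjusted analysis is biased, that the analyses were not prespecified, or that the interaction rule is an error.

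**What to change.** In Section 10, Aim 1:

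- Name the planned GEE model with baseline score and age as the primary analysis of each scale, and the model without them as supportive.
- Justify the adjustment by precision as well as by chance imbalance.
- State that the outcome is the 3-month score.
- State that the references to Aim 1 under Objective 2 keep their present meaning, so that adjustment stays exploratory there. Without this sentence the edit would carry over to the retention, drug-level and adherence outcomes.
- Leave the p ≥ 0.20 rule for the combined effect as it is.

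The cost is a few sentences of analysis-plan wording. No new data, participants or models are needed. The statistical cost is the 1 to 1.5% larger standard error if baseline and 3-month scores prove almost uncorrelated.
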